| 15.5 | Study Records Retention | 45 |
| 15.6 | Protocol Deviations | 45 |
| 16 | Publication Policy | 46 |
| 17 | Literature References | 47 |
| | Appendix A: Schedule of Events | 49 |

[figure not shown]
LIST OF ABBREVIATIONS

| | |
|-------------|--|
| BV | Bacterial Vaginosis |
| CDC | Centers for Disease Control and Prevention |
| CFR | Code of Federal Regulations |
| CRF | Case Report Form |
| DHHS | Department of Health and Human Services |
| DMID | Division of Microbiology and Infectious Diseases, NIAID, NIH, DHHS |
| DNA | Deoxyribonucleic Acid |
| eCRF | Electronic Case Report Form |
| gyrA | Gyrase A Genotype |
| ICH | International Council for Harmonisation |
| ICMJE | International Committee of Medical Journal Editors |
| IEC | Independent or Institutional Ethics Committee |
| IRB | Institutional Review Board |
| ITT | Intent-to-Treat |
| MIC | Minimum Inhibitory Concentration |
| micro-ITT | Microbiological Intent-to-Treat |
| NAAT | Nucleic Acid Amplification Test |
| NIAID | National Institute of Allergy and Infectious Diseases, NIH, DHHS |
| NIH | National Institutes of Health |
| OHRP | Office for Human Research Protections |
| PCR | Polymerase Chain Reaction |
| PP | Per-Protocol |
| QA | Quality Assurance |
| QC | Quality Control |
| SDCC | Statistical Data and Coordinating Center |
| SOP | Standard Operating Procedure |
| STD | Sexually Transmitted Disease |

PROTOCOL SUMMARY

| | |
|---|---|
| Title: | Clinical Validation of a Molecular Test for Ciprofloxacin-Susceptibility in Neisseria gonorrhoeae |
| Population: | Approximately 381 subjects will be enrolled to identify approximately 257 per protocol eligible subjects diagnosed with untreated serine 91 gyrase A genotype Neisseria gonorrhoeae of the rectum, or male or female urogenital tract |
| Number of Sites: | Up to eight sites in the United States |
| Study Duration: | Approximately 30 months after enrollment of the first subject |
| Subject Participation Duration: | 11-14 days per subject |
| Description of Agent or Intervention: | Directly observed treatment with a single dose of ciprofloxacin 500 mg orally for Neisseria gonorrhoeae infections deemed serine 91 gyrase A genotype by real-time polymerase chain reaction with fluorescent hybridization probe detection of sequence |
| Objectives: | 
Primary: To determine the efficacy of ciprofloxacin for treatment of uncomplicated Neisseria gonorrhoeae infections with gyrA serine 91 genotype
 
Secondary: To investigate efficacy of ciprofloxacin for treatment of uncomplicated serine 91 gyrase A genotype Neisseria gonorrhoeae infection by anatomic site To determine the sensitivity of the gyrase A assay for detection of ciprofloxacin-susceptible Neisseria gonorrhoeae infections
 |
| Description of Study Design: | See Schematic |
| Estimated Time to Complete Enrollment: | Approximately 24 months |

Schematic

2 BACKGROUND INFORMATION AND SCIENTIFIC RATIONALE

2.1 Background Information

Gonorrhea is the second most commonly reported notifiable disease in the United States with more than 330,000 cases reported in 2012, a rate of 107.5 per 100,000 population [1]. Over the past 75 years, *Neisseria gonorrhoeae* (*N. gonorrhoeae*) infections have become increasingly resistant to antimicrobial therapy, first to sulfa-based antibiotics, then penicillins, tetracyclines, fluoroquinolones, and now extended-spectrum cephalosporins [2]. Prior to the advent of ciprofloxacin-resistant *N. gonorrhoeae*, ciprofloxacin was the primary first-line recommended therapy for *N. gonorrhoeae* infections of the throat, rectum, urethra, and cervix. From 1998 to 2006, ciprofloxacin was the Centers for Disease Control and Prevention (CDC) recommended treatment for *N. gonorrhoeae* in all anatomic sites. Prior to widespread ciprofloxacin resistance, the efficacy of ciprofloxacin treatment in susceptible *N. gonorrhoeae* infections was estimated at more than 99% [3-4]. In 2007, due to high rates of ciprofloxacin resistance in *N. gonorrhoeae* nationally, the CDC recommended the discontinuation of ciprofloxacin treatment for gonorrhea, which was followed by a decline in ciprofloxacin *N. gonorrhoeae* resistance nationally [5]. At this time, the only recommended treatment for *N. gonorrhoeae* infection is dual antibiotic therapy with injectable ceftriaxone and oral azithromycin or doxycycline [6].

For decades, bacterial culture was the standard diagnostic modality for *N. gonorrhoeae* infections. Culture is specific, but studies have demonstrated that the molecular-based enzyme immunoassay or nucleic acid amplification test (NAAT) has a higher clinical sensitivity than culture [7]. However, there has not been a widely used and reliable technology that allows for antibiotic susceptibility testing from non-culture specimens.

It has been recently demonstrated that *N. gonorrhoeae*-deoxyribonucleic acid (DNA) mutations can be detected using modern molecular techniques and real-time polymerase chain reaction (PCR) assays can be used to detect reproducible, clinically significant resistance [8-10]. A protocol for the detection of alterations in the gyrase A gene (*gyrA*), the target of ciprofloxacin anti-gonococcal activity, has been validated [8]. While molecular markers of susceptibility have high concordance, sensitivity and a specificity of 93% and 100%, respectively, compared with standard antimicrobial susceptibility testing, the clinical performance of the test and the response to therapy based on a molecular susceptibility result in *N. gonorrhoeae* is unknown.

2.2 Rationale

Resistance to extended-spectrum cephalosporins was first identified in Japan and is increasing in the western United States and among men who have sex with men [11]. Antimicrobial resistance mechanisms have been fairly well described as mutations in target proteins, alterations in cell wall components, or increases in efflux pumps [2].

Currently, the nationwide frequency of *N. gonorrhoeae* isolates with decreased ciprofloxacin susceptibility, minimum inhibitory concentration (MIC) ≥ 0.125 $\mu\text{g/mL}$, or resistance (MIC ≥ 0.5 $\mu\text{g/mL}$) is relatively modest at 13.5% [12]. Prior experience with changing antibiotic treatment guidelines has demonstrated that major shifts in antibiotic use may modify the ecology of drug resistance. For example, restricting erythromycin use in Group A streptococcal infections in Finland led to a population-level decrease in erythromycin-resistance in that organism [13].

While molecular methods to diagnose *N. gonorrhoeae* have greatly improved the detection of infection [14], they have historically precluded the ability to perform antibiotic susceptibility testing. Although regional surveillance data critically inform treatment recommendations, those data cannot be used for real-time individualized clinical management. The clinical validation of an assay to determine the ciprofloxacin susceptibility of *N. gonorrhoeae* infections could result in increased use of ciprofloxacin for ciprofloxacin-susceptible *N. gonorrhoeae* infections and resultant decreased use of extended-spectrum cephalosporins, thereby reducing the selection pressure for cephalosporin resistance in *N. gonorrhoeae*. An immediate benefit to taking ciprofloxacin would be for those with cephalosporin allergies who would have to take combination therapy that is more difficult to administer.

2.3 Potential Risks and Benefits

2.3.1 Potential Risks

Performance of the assay

Clinical specimens will be tested for a molecular marker of ciprofloxacin susceptibility. Treatment decisions will be made by the subject's clinician, per standard protocols, based on interpretation of laboratory results and selection of the best course of treatment based on available information. There is a small risk of a misclassification of susceptibility if the test were to show that the *N. gonorrhoeae* infection is ciprofloxacin-susceptible when in fact, it is resistant, and a subject with ciprofloxacin-resistant *N. gonorrhoeae* infection would not receive the appropriate treatment. The risk would be ameliorated if the test of cure visit (Visit 2, Day 5-10) displayed a treatment failure and the subject received standard treatment. The risk would therefore be that this would result in a delay of effective treatment.

The risk of a *N. gonorrhoeae* false negative test of cure result is estimated to be less than 0.5% and would result in inappropriate treatment for a subject with ciprofloxacin-resistant *N. gonorrhoeae* infection [9]. The risks of treatment failure include continued symptoms and potential transmission of *N. gonorrhoeae* to partners. Without effective re-treatment, treatment failure might result in complications including pelvic inflammatory disease, ectopic pregnancy,

infertility, chronic pelvic pain, and increased risk of transmission and HIV infection.

Risks from study procedures

Subjects may become embarrassed, worried, or anxious when discussing their sexual practices or ways for protecting against HIV and other infections passed during sex. They may also experience anxiety while they await test results. Women may expect to feel a little discomfort during the speculum exam. Subjects may experience gagging, discomfort, fainting, or bleeding when swabs are collected from the throat, rectum, urethra or cervix.

Risks of ciprofloxacin

Ciprofloxacin may cause dizziness, nervousness, difficulty sleeping, or increased sensitivity to sunlight, possibly resulting in sunburn. Like many antibiotics used to treat infections, ciprofloxacin may cause nausea, vomiting, stomach pain, headaches, tiredness, pale skin or a mild skin rash. Less often, hearing loss, kidney, liver or nerve problems, tendon pain, an irregular heartbeat, or fainting may occur. It is not known if ciprofloxacin will harm a fetus. Pregnancy tests can miss the first 14 days of pregnancy; therefore, fetuses may be exposed to ciprofloxacin if a subject's pregnancy is undetected at enrollment.

Significant side effects of ciprofloxacin

Significant side effects are rare, estimated to be less than 2%, and may include severe skin rash; hives; itching; difficulty breathing or swallowing; swelling of the face, throat, tongue, lips, eyes, hands, feet, ankles, or lower legs; hoarseness; yellowing of the skin or eyes; and rapid, pounding, or irregular heartbeat.

Unknown risks

There may be unknown risks that cannot be foreseen.

2.3.2 Known Potential Benefits

There are no known benefits to individual subjects. A potential benefit to future *N. gonorrhoeae*-susceptible infected individuals is treatment with a less invasive regimen (orally administered vs. intramuscular injection), which is less painful. Results from this study may help gonorrhea-infected individuals by reducing drug resistance as a result of the use of the most appropriate treatment, which is guided by pretreatment determination of ciprofloxacin-susceptible gonococcal infection.

The study will help to assess the potential impact of a strategy to address the critical problem of emerging drug resistance in *N. gonorrhoeae*. Specifically, the information gained from this study can be used to influence national sexually transmitted disease (STD) treatment policies and, therefore, result in a marked

decrease in extended-spectrum cephalosporin-resistant *N. gonorrhoeae* infection, improving the availability of treatment options for individuals infected with *N. gonorrhoeae*.

This study may provide an alternative regimen for the treatment of gonorrhea in cases of cephalosporin allergy or antimicrobial resistance to cephalosporins. It may also provide an oral regimen for settings in which injections are not feasible. In addition, it may provide a convenient and easy-to-administer patient-delivered therapy for the partners of index cases.

3 OBJECTIVES

3.1 Study Objectives

3.1.1 Primary Objective

To determine the efficacy of ciprofloxacin for treatment of uncomplicated *N. gonorrhoeae* infections with *gyrA* serine 91 genotype

3.1.2 Secondary Objectives

- 1) To investigate the efficacy of ciprofloxacin for treatment of uncomplicated serine 91 *gyrA* *N. gonorrhoeae* infection by anatomic site
- 2) To determine the sensitivity of the *gyrA* assay for detection of ciprofloxacin-susceptible *N. gonorrhoeae* infections

3.1.3 Exploratory Objectives

- 1) To characterize *N. gonorrhoeae* isolates and non-*gyrA* gene-dependent mechanisms of ciprofloxacin resistance post-treatment of uncomplicated *N. gonorrhoeae* infection by anatomic site using traditional and molecular methods like genotyping and sequencing
- 2) To investigate the efficacy of ciprofloxacin for treatment of uncomplicated serine 91 *gyrA* *N. gonorrhoeae* infections by demographic and clinical characteristics

3.2 Study Outcome Measures

3.2.1 Primary Outcome Measure

The proportion of subjects infected with *gyrA* serine 91 genotype *N. gonorrhoeae* with microbiological cure at Visit 2 (Day 5-10)

3.2.2 Secondary Outcome Measures

- 1) The proportion of subjects infected with *gyrA* serine 91 genotype *N. gonorrhoeae* with microbiological cure at each anatomic site (throat, rectum, male or female urogenital tract) at Visit 2 (Day 5-10)
- 2) The proportion of subjects infected with *gyrA* serine 91 genotype *N. gonorrhoeae* identified by *gyrA* gene PCR who have ciprofloxacin-susceptible *N. gonorrhoeae* as identified by culture-based antimicrobial susceptibility testing at Visit 1 (Day 1)

3.2.3 Exploratory Outcome Measures

- 1) Identification and characterization of non-*gyrA* gene-dependent mechanisms of ciprofloxacin resistance by genotyping and whole genome sequencing (e.g., Illumina) of nucleic acid isolated from uncured subjects at Visit 2 (Day

5-10). Genotyping and sequencing may be performed on nucleic acid isolated from different anatomic sites.

- 2) The proportion of subjects infected with *gyrA* serine 91 genotype *N. gonorrhoeae* with microbiological cure at Visit 2 (Day 5-10) by demographic and clinical characteristics

4 STUDY DESIGN

This study is a multi-center, single-arm, open-label clinical study to assess the efficacy of one dose of ciprofloxacin given orally in subjects infected with untreated *gyrA* serine 91 genotype *N. gonorrhoeae* as determined by a real-time PCR assay. The study will enroll approximately 381 subjects to obtain a per protocol eligible target of 257 subjects age 18 years or older regardless of gender identification who are seeking care in STD clinics at participating sites in the United States. Subjects who have untreated *gyrA* serine 91 genotype *N. gonorrhoeae* of the rectum, or male or female urogenital tract identified by a positive culture or NAAT conducted at a prior visit will be offered enrollment in the study. Subjects not consenting to participate in the study will receive treatment per local standard of care.

At enrollment, Visit 1 (Day 1), a brief physical exam and medical and sexual history will be done. Subjects will have samples collected for *N. gonorrhoeae* culture and *N. gonorrhoeae* NAAT (to include *gyrA* serine 91 genotype) from each infected anatomic site (throat, rectum, male or female urogenital tract) to verify infection status.

Subjects with *gyrA* serine 91 genotype rectal or urogenital *N. gonorrhoeae* will receive one dose of directly observed ciprofloxacin 500 mg. Subjects will be observed in the clinic for at least 5 minutes after receiving ciprofloxacin and will be instructed to return to the clinic or to contact the study site coordinator immediately if they vomit within 1 hour of receiving ciprofloxacin. Subjects who vomit within 1 hour of study drug administration should be retreated for *N. gonorrhoeae* infection with an alternative recommended regimen per local standard of care.

Subjects will return for clinical and laboratory assessments at Visit 2 (Day 5-10), test of cure visit. Subjects will have repeat samples collected for *N. gonorrhoeae* culture and *N. gonorrhoeae* NAAT from all anatomic sites swabbed at Visit 1 (Day 1).

For Visit 3 (Day 11-14), test results will be provided to subjects by phone call. No further follow-up is required for subjects who test culture negative and NAAT negative. Subjects who test culture positive or NAAT positive will be referred for standard of care treatment for *N. gonorrhoeae*.

The duration of the study for each subject will be approximately 11-14 days. Study enrollment is expected to be completed in 24 months.

5 STUDY ENROLLMENT AND WITHDRAWAL

5.1 Subject Inclusion Criteria

Subjects must meet all of the inclusion criteria in order to be eligible to participate in the study. Subjects who present with a new *N. gonorrhoeae* infection may be rescreened for eligibility. No exemptions are granted on Subject Inclusion/Exclusion Criteria in DMID-sponsored studies.

1. Willing and able to give voluntary written informed consent before any study related procedure is performed.
2. 18 years or older on the day of enrollment.
3. Untreated *gyrA* serine 91 genotype *N. gonorrhoeae* of the rectum, or male or female urogenital tract*, as determined by the *gyrA* test assay on a specimen collected within 30 days of enrollment.
*Subjects must have *gyrA* serine 91 genotype detected for *N. gonorrhoeae* from at least one non-pharyngeal site.
4. Willing to abstain from sexual intercourse or use condoms during any sexual contact until the Test of Cure Visit (Visit 2, Day 5-10) is complete.
5. Women of childbearing potential* must have no vaginal intercourse 14 days before enrollment or use an effective birth control method ** for 30 days before enrollment and agree to continue through visit 2.
*A woman is considered of childbearing potential unless post-menopausal (>2 years) or surgically sterilized (tubal ligation >1 year, bilateral oophorectomy, or hysterectomy).
**Acceptable birth control methods for the purposes of this study may include abstinence from intercourse with a male partner, monogamous relationship with vasectomized partner, male condoms with the use of applied spermicide, intrauterine devices, and licensed hormonal methods. A highly effective method of contraception is defined as one that results in a low failure rate (i.e., less than 1% per year) when used consistently and correctly.
6. Able to swallow pills.
7. Willing to comply with protocol requirements, including availability for follow-up for the duration of the study.
8. Agree to avoid systemic or intravaginal antibiotics* with activity against *N. gonorrhoeae* from enrollment through Visit 2 (Day 5-10). *Topical and intravaginal antifungals are permitted.
9. Agree to avoid magnesium/aluminum antacids, sucralfate, didanosine, or highly buffered drugs, up to 2 hours after receipt of study drug.

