7.1 Visit 1, Day 1 (Screening/Enrollment)

Screening and enrollment will occur at the same clinic visit. Potential subjects will be informed about the study and invited to participate. Subjects who are interested in the study will be asked to sign a consent form that will describe the purpose of the study, the procedures to be followed, the risks and benefits of participating, and will include a separate section for consent to store samples for future use. A copy of the consent form will be given to the subject and this fact will be documented in the CRF.

The following will be performed for subjects who give informed consent:

1. Demographic information including age, sex, and gender will be collected from the subject
2. Eligibility criteria will be reviewed with the subject
3. Discuss pertinent medical history for assessment of specific symptoms that are potentially related to fluoroquinolone use as described in section 9, Assessment of Safety, and sexual history will be obtained by interview of subjects to assure eligibility. Concomitant infections will be reviewed.
4. Review of signs and symptoms within the past 7 days
5. All new antibiotics or concomitant medications contraindicated with ciprofloxacin taken in the 30 days prior to signing the informed consent will be recorded on the appropriate data collection form
6. Targeted physical exam
7. Speculum exam for females
Note: Women diagnosed with BV by local standard test at Visit 1 will receive treatment for BV at Visit 2 according to local standard of care.
8. Urine pregnancy test for females of childbearing potential
9. One swab for *N. gonorrhoeae* culture and one swab for NAAT and *gyrA* serine 91 genotype from the throat*
10. One swab for *N. gonorrhoeae* culture and one swab for NAAT and *gyrA* serine 91 genotype from the rectum*
11. One swab for *N. gonorrhoeae* culture from the urethra (males)*
12. Urine specimen for NAAT and *gyrA* serine 91 genotype (males)*
13. Cervical swab for *N. gonorrhoeae* culture (females)*
14. Cervical or vaginal swab for NAAT and *gyrA* serine 91 genotype (females)*
*Note 1: Only at the suspected infected anatomical site based on prior test results or other sites as clinically indicated
*Note 2: *GyrA* assay is required only if NAAT is positive

-

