11.4.3.2 Secondary Analyses

The analysis of the efficacy of by anatomic site (secondary objective 1) will proceed as described in section 11.4.3.1 where the modification to

the definition of microbiological outcome status is provided below. Summaries of the cure rate estimate and associated confidence interval and hypothesis test will be generated for each individual anatomic site.

For the analysis of secondary objective 1, microbiological outcome status at each anatomical site is evaluated at Visit 2 (Day 5-10) and is defined for a particular anatomical site as follows:

- Microbiological Cure: *N. gonorrhoeae* not detectable by culture at the particular anatomical site that had detectable *N. gonorrhoeae* at Visit 1.
- Microbiological Failure: *N. gonorrhoeae* detectable by culture at the particular anatomical site that had detectable *N. gonorrhoeae* at Visit 1.
- Non-evaluable: At least one of the following: Subject did not return for Visit 2 (Day 5-10), or culture results at Visit 2 (Day 5-10) were not available for any reason, or subject could not be evaluated for microbiological outcome status for any other reason.

For the analysis of the sensitivity of the *gyrA* assay for the detection of ciprofloxacin-susceptible *N. gonorrhoeae* infections (secondary objective 2), the sensitivity will be estimated by calculating the proportion of enrolled subjects who have ciprofloxacin-susceptible *N. gonorrhoeae* as identified by culture-based antimicrobial susceptibility testing at Visit 1. The proportion of enrolled subjects who do not have ciprofloxacin-susceptible *N. gonorrhoeae* will also be estimated. This analysis will be performed in the micro-ITT analysis population. Secondary and sensitivity analyses, which will assess the impact of analysis population and missing antimicrobial susceptibility testing, may be performed. These analyses will be specified in the separate statistical analysis plan document.

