3.3.3. Sensitivity of the *gyrA* assay

For the analysis of the sensitivity of the *gyrA* assay for the detection of ciprofloxacin-susceptible *N. gonorrhoeae* infections (secondary objective 2), two measures will be estimated. First, the sensitivity of the assay will be estimated using the following (overall and separately for each anatomical site):

True Positives (TP): the number wild type *gyrA* infections that are ciprofloxacin-susceptible *N. gonorrhoeae* as identified by culture-based antimicrobial susceptibility testing at Visit 1.

False Negatives (FN): the number of non-wild type *gyrA* infections that are ciprofloxacin-susceptible *N. gonorrhoeae* as identified by culture-based antimicrobial susceptibility testing at Visit 1.

$$\text{Sensitivity} = \text{TP} / (\text{TP} + \text{FN})$$

Given the design of the study, the estimate of sensitivity may be biased because subjects with no wild type infections are not enrolled and thus their samples are not tested for culture-based susceptibility testing. To supplement the estimates of sensitivity, the assay's positive predictive value (PPV) will also be estimated. PPV is calculated using the following (overall and separately for each anatomical site):

True Positives (TP): the number wild type *gyrA* infections that are ciprofloxacin-susceptible *N. gonorrhoeae* as identified by culture-based antimicrobial susceptibility testing at Visit 1.

False Positives (FP): the number of wild type *gyrA* infections that are not ciprofloxacin-susceptible *N. gonorrhoeae* as identified by culture-based antimicrobial susceptibility testing at Visit 1.

$$\text{PPV} = \text{TP} / (\text{TP} + \text{FP}).$$

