14. TECHNICAL DETAILS

SAS version 9.4 or above will be used to generate all tables, figures, and listings.

**15. SUMMARY OF CHANGES IN THE CONDUCT OF THE STUDY OR
PLANNED ANALYSES**

There are no changes in the planned analyses.

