Intent-to-Treat (ITT) Population	Number of Infections with Microbiological Cures, n	x	x	x	x
	Number of Infections, N	x	x	x	x
	Microbiological Cure Rate, %	xx.x	xx.x	xx.x	xx.x
	95% CI, %	xx.x, 100	xx.x, 100	xx.x, 100	xx.x, 100
Microbiological Intent-to-Treat (micro-ITT) Population	Number of Infections with Microbiological Cure, n	x	x	x	x
	Number of Infections, N	x	x	x	x
	Microbiological Cure Rate, %	xx.x	xx.x	xx.x	xx.x
	95% CI, %	xx.x, 100	xx.x, 100	xx.x, 100	xx.x, 100
Per-Protocol (PP) Population	Number of Infections with Microbiological Cure, n	x	x	x	x
	Number of Infections, N	x	x	x	x
	Microbiological Cure Rate, %	xx.x	xx.x	xx.x	xx.x
	95% CI, %	xx.x, 100	xx.x, 100	xx.x, 100	xx.x, 100

Implementation Notes: The ITT Population, Micro-ITT Population and PP Population will be based on the anatomical site.

Table 12: Summary of *gyrA* Assay Results and Culture-Based Antimicrobial Susceptibility Testing at Visit 1—ITT population

	Anatomic Site		Culture-Based Antimicrobial Susceptibility Testing					
			Susceptible		Not Susceptible		Total	
			n	%	n	%	n	%
gyrA Assay	All Sites	Wild Type gyrA detected	xx	xx	xx	xx	xx	xx
		Mutant gyrA detected	xx	xx	xx	xx	xx	xx
		Total	xx	xx	xx	xx	xx	100
	Urethral	Wild Type gyrA detected	xx	xx	xx	xx	xx	xx
		Mutant gyrA detected	xx	xx	xx	xx	xx	xx
		Total	xx	xx	xx	xx	xx	100
	Cervical	Wild Type gyrA detected	xx	xx	xx	xx	xx	xx
		Mutant gyrA detected	xx	xx	xx	xx	xx	xx
		Total	xx	xx	xx	xx	xx	100
	Rectal	Wild Type gyrA detected	xx	xx	xx	xx	xx	xx
		Mutant gyrA detected	xx	xx	xx	xx	xx	xx
		Total	xx	xx	xx	xx	xx	100
	Pharyngeal	Wild Type gyrA detected	xx	xx	xx	xx	xx	xx
		Mutant gyrA detected	xx	xx	xx	xx	xx	xx
		Total	xx	xx	xx	xx	xx	100

The denominator for percentages is based on the number of instances in which swabs taken from a subject at Visit 1 resulted in a determinate *gyrA* Assay result and a determinate culture-based antimicrobial susceptibility test result. If either *gyrA* Assay result or culture-based antimicrobial susceptibility test result is indeterminate or missing, both results will be excluded. Susceptible is defined as an MIC of < 1 ug/ml as reported by the antimicrobial susceptibility testing.

Implementation Notes: The ITT Population will be based on the anatomical site.

Table 13: Culture Results by Time Point and Anatomical Sites

Time Point	Result	Urethral (N=X)		Cervical (N=X)		Rectal (N=X)		Pharyngeal (N=X)	
		n	%	n	%	n	%	n	%

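### The SAP computes the gyrA assay's PPV from the Visit 1 repeat, not from the qualifying result that led to dosing; both should be reported

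*Protocol*

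**What the plan says.** - **Who is dosed.** Protocol 4 offers enrollment to subjects whose infection was "identified by a positive culture or NAAT conducted at a prior visit will be offered enrollment in the study". Inclusion criterion 3 (Protocol 5.1) requires a wild-type result, "as determined by the *gyrA* test assay on a specimen collected within 30 days of enrollment". Exclusion criterion 9 (Protocol 5.2) rules out a mutant result at any site in the same window.
- **When.** Protocol 7.1 states: "Screening and enrollment will occur at the same clinic visit". New swabs are taken, and the dose follows once they are collected and eligibility has been assessed. No step waits for a gyrA result from those swabs, and the assay is required on them only if NAAT is positive.
- **Protocol analysis.** In Protocol 11.4.3.2, "the sensitivity will be estimated by calculating the proportion of enrolled subjects who have ciprofloxacin-susceptible *N. gonorrhoeae" by culture-based testing at Visit 1. The population is micro-ITT, which Protocol 11.4.1 defines by Day 1 culture, with no condition on a Visit 1 gyrA result.
- **SAP analysis.** SAP 3.3.3 adds PPV = TP/(TP + FP), with "False Positives (FP): the number of wild type *gyrA* infections that are not ciprofloxacin-susceptible" by Visit 1 culture. That section does not name the specimen behind the wild-type call, but SAP 3.3.1 takes wild type from the Visit 1 swab. The Table 12 footnote limits the table to cases where "swabs taken from a subject at Visit 1 resulted in a determinate *gyrA* Assay result and a determinate culture-based antimicrobial susceptibility test result". SAP 6.5 drops a specimen when either result is indeterminate or missing. SAP 8.2 uses the ITT population.
- **Stated changes.** SAP 15: "There are no changes in the planned analyses".

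**The concern.** The test that sends a subject to ciprofloxacin is the qualifying assay. Protocol 2.3.1 names the risk attached to it: a susceptible call on an infection that is in fact resistant. Secondary endpoint 2 is where the trial would measure how often that happens, and the SAP scores a different test there, the repeat taken on the day of dosing.

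A user of the assay would act on one call and would not have a second before treating. A PPV that drops a resistant infection because a second assay read it as mutant does not describe that use. SAP 3.3.3 warns of bias for sensitivity only and offers PPV as the supplement, without a similar caution. The qualifying result appears in none of Table 12, Table 15 or Listing 5, so the planned outputs would not show how often the two calls differ.

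**Working it through.** **1. Denominator.** The documents give no PPV figure, so I take a denominator from the sample size section (Protocol 11.2, SAP 5). With 25% culture negative and 10% otherwise excluded, 257/(0.75 × 0.90) = 380.7, which reproduces the 381 stated. Culture-positive subjects: 381 × 0.75 = 285.75, about 286. I assume one infected site each and a determinate susceptibility and repeat result for all.

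**2. Accounting.** Let N = 286 and let r be the resistant Visit 1 isolates. Let m be those of the r that the repeat reads as mutant, and s the susceptible isolates that it reads as mutant.

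- PPV of the qualifying call = (N − r)/N
- PPV under SAP 3.3.3 = (N − r − s)/(N − m − s)

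The m infections sit in Table 12's mutant, not-susceptible cell. They are neither true nor false positives, so they leave numerator and denominator together.

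**3. Bound.** For x of n, the lower bound is the 0.05 quantile of Beta(x + 0.5, n − x + 0.5), or 0.05^(1/n) when x = n. Protocol 11.4.3.1 prints 0.95 as the quantile; a lower bound needs 0.05, which is what the SAP 6.1.1 code with alpha = 0.1 gives.

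**4. Resistant isolates re-read as mutant (s = 0).** Values of r and m are assumed; the documents give neither.

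| r | Qualifying call (bound) | SAP, some re-read mutant (bound) | SAP, all re-read mutant (bound) |
|---|---|---|---|
| 3 | 283/286 = 98.95% (97.56) | m = 2: 283/284 = 99.65% (98.63) | 283/283 = 100% (98.95) |
| 6 | 280/286 = 97.90% (96.13) | m = 3: 280/283 = 98.94% (97.53) | 280/280 = 100% (98.94) |
| 10 | 276/286 = 96.50% (94.36) | m = 5: 276/281 = 98.22% (96.53) | 276/276 = 100% (98.92) |

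Each such isolate adds about 1/286 = 0.35 percentage points. With m = 0 the two PPVs are equal.

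**5. Susceptible isolates re-read as mutant.** With r = 6, m = 0 and s = 10, the SAP PPV is 270/276 = 97.83%, against 97.90% on the qualifying call. Ten of these lower PPV by less than 0.1 point. They also become false negatives in the sensitivity estimate.

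**6. Missing repeats.** The Visit 1 gyrA assay is required only after a positive NAAT (Protocol 7.1), and Protocol 8.2.2 foresees a negative NAAT with a positive culture. Such a subject can have a qualifying call and a susceptibility result and still leave the PPV. The direction depends on whether the isolate is resistant.

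**The case against.** Same-visit pairing of test and reference is a standard accuracy design. A call up to 30 days old set against a Day 1 isolate mixes assay error with change of strain, and a strain acquired in between is not an assay failure. The protocol does not say outright that the qualifying specimen is the index test: outcome measure 2 in Protocol 3.2.2 mentions gyrA PCR without naming a specimen, and Protocol 4 has Visit 1 genotyping done to verify infection status. This stands as a reason to keep the same-day PPV. It does not make that PPV a measure of the call that led to dosing.

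Table 12's Total row already gives susceptible over all instances with both results determinate. In the simplified example above it would print 280/286 = 97.9%. A reader might infer that the SAP hides this quantity; it does not. But the row is not labelled as the protocol's estimate, carries no confidence bound, pools sites that may have no qualifying call, and omits subjects without a determinate repeat.

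Three further inferences are tempting and not supported:

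- *The PPV credits the assay with a correct call on these infections.* It does not; they leave the calculation. Only their cell in Table 12 is concordant, and no specificity or negative predictive value is planned.
- *The method can only favour the assay.* That holds for resistant isolates. Susceptible isolates re-read as mutant lower PPV, and missing repeats can act either way.
- *The mutant rows of Table 12 exist only because repeats may differ.* Only one non-pharyngeal site has to qualify, and Visit 1 samples other sites as clinically indicated, so those rows may also hold sites with no qualifying call.

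Finally, Protocol 2.1 cites 93% sensitivity and 100% specificity for molecular markers of susceptibility. Read with susceptible as the positive result, resistant infections called wild type would be rare and the effect near zero. That may prove true, but the same paragraph calls clinical performance unknown.

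**Conclusion.** The point holds for secondary endpoint 2. Dosing rests on the qualifying call; the planned PPV rests on the Visit 1 repeat and so measures same-day agreement. The protocol's quantity, the proportion of enrolled subjects with a susceptible Visit 1 isolate, has been replaced and the population changed from micro-ITT to ITT, yet SAP 15 reports no change.

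The size cannot be determined from the documents. Under the assumptions above it is about 0.35 points upward per resistant isolate re-read as mutant, a much smaller downward shift per susceptible isolate re-read as mutant, and nothing if no repeat reads mutant. The larger gaps require most or all resistant isolates to re-read as mutant, for which the documents give no rate. No threshold or test is attached to PPV, and the sample size does not depend on it. The change is nevertheless worth making: it restores a protocol-specified estimate at little cost.

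**What to change.** - Keep the same-day Visit 1 PPV in SAP 3.3.3, 8.2 and Table 12, labelled as same-day agreement.
- Beside it, report the PPV of the qualifying call with the modified Jeffreys bound. Denominator: enrolled subjects (and, by site, sites with a qualifying wild-type call) that have a determinate Visit 1 susceptibility result, whatever the repeat reads. Numerator: those that are susceptible. Do not restrict it to the SAP's micro-ITT population, which requires wild type on Day 1 and would bring the repeat back in.
- Add a table of qualifying against Visit 1 gyrA calls, with days between specimens, and add the qualifying result to Listing 5.
- Record the departure from Protocol 11.4.3.2 in SAP 15.

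The cost is SAP and shell wording, one table and one listing field; no new specimens or visits. There are two downsides. The qualifying-call PPV mixes assay error with strains acquired between specimens, so it may be slightly lower; the concordance table by interval helps to judge this. It also needs the qualifying result and specimen date, by site, as analysable data. They are needed to confirm eligibility, but the documents do not show that they are captured in that form, so this should be checked first.
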